## 14.3 Analysis of Secondary Endpoints

The secondary endpoints include Time to first cytotoxic treatment (TFCT), progression free survival (PFS) and overall survival (OS). For those time-to-event endpoints, Kaplan-Meier method and Cox proportional hazard model will be used for the data analysis. Potential prognostic factors will be correlated with conversion status by Fisher's exact test or Chi-square test, logistic regression will be used to assess the effect on conversion from the combination of multiple factors.

## 14.4 Reporting and Exclusions

#### 14.4.1 Evaluation of toxicity:

All patients will be evaluable for toxicity from the time of their first treatment. All patients treated with curcumin and vitamin D3 will be included in safety summaries and analyses from the time of first treatment. The safety and tolerability of curcumin and vitamin D3 will be CASE 5913 55 of 74 Protocol Version 7 Dated 10/2/2018 examined by: extent of exposure to treatment (dose, duration, and number of patients), and a detailed examination of adverse events, laboratory test results, vital signs, and physical findings.

Our planned sample number is 35 evaluable patients, but if there is evidence of toxicity as high as 20% DLTs the study will be terminated within the first 20 patient cohort. If ever 2 of the initial 10 patients exhibit DLT the study will be terminated. If ever 5 of the entire 35 patients exhibit DLT the treatment will be considered too toxic. These rules imply 84% power with 9.9% type I error to distinguish a 20% DLT rate from one not over 8%. The chance of early termination under the hypothesis of 20% DLT is 37%. The chance of early termination in error is 1.8%.

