#### 3.2 Number of Subjects

We plan to enroll a maximum of 35 patients to obtain 29 evaluable patients (assuming a 20% dropout rate).

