## 13.2.5 Audits and inspections

Authorized representatives of the sponsor, a regulatory authority, an Independent Ethics Committee (IEC) or an Institutional Review Board (IRB) may visit the Center to perform audits or inspections, including source data verification. The purpose of an audit or inspection is to systematically and independently examine all study-related activities and documents to determine whether these activities were conducted, and data were recorded, analysed, and accurately reported according to the protocol, Good Clinical Practice (GCP), guidelines of the International Conference on Harmonization (ICH), and any applicable regulatory requirements.

*13.2.6 Data Safety and Monitoring Plan* This protocol will adhere to the policies of the Case Comprehensive Cancer Center Data and

Safety Monitoring Plan in accordance with NCI regulations.

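### The DLT limits in section 14.4.1 do not have the error rates stated for them: exact type I error is 25.9%, not 9.9%, and early termination in error is about 19%, not 1.8%

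*Combined protocol and SAP*

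**What the plan says.** Section 14.4.1 of the combined protocol and SAP makes three statements about DLTs.

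- A rate clause: if there is "evidence of toxicity as high as 20% DLTs the study will be terminated within the first 20 patient cohort". No count is attached.
- An early limit: "If ever 2 of the initial 10 patients exhibit DLT the study will be terminated".
- An overall limit: "If ever 5 of the entire 35 patients exhibit DLT the treatment will be considered too toxic". No action is attached.

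It then attributes error rates to them: "These rules imply 84% power with 9.9% type I error to distinguish a 20% DLT rate from one not over 8"%. It adds "The chance of early termination under the hypothesis of 20% DLT is 37"% and "The chance of early termination in error is 1.8"%.

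The section describes the 35 as evaluable patients. Section 3.2 differs: "We plan to enroll a maximum of 35 patients to obtain 29 evaluable patients". Section 10.5 records that accrual closed on 4/12/2016. The current protocol version is dated 10/2/2018.

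**The concern.** The four percentages are presented as consequences of the limits just listed, so they should follow from those limits by binomial arithmetic. A rough check already raises doubt. Two or more DLTs among 10 patients is not rare when the true rate is 8%, yet the plan puts early termination in error at 1.8%.

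At stake is the weight of a toxicity finding. Tolerability is part of the general objective in section 2.0. A reader of 14.4.1 would believe that a regimen at the acceptable 8% rate is wrongly condemned in about 1 trial in 10, and wrongly stopped early in about 1 in 50. If the true chances are several times larger, a stop or an adverse verdict under these rules says less about the regimen than the plan claims.

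**Working it through.** **Inputs, all from section 14.4.1.** Acceptable DLT rate 8%, unacceptable rate 20%. Limits 2 of 10 and 5 of 35. Stated results 84%, 9.9%, 37% and 1.8%. DLTs are taken as independent and entry as sequential. X10 is the number of DLTs in the first 10 patients, and Y25 the number in the next 25.

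**Step 1: try to reproduce the stated figures from the printed limits.** A trial is flagged if it has 2 or more DLTs in the first 10 or reaches 5 in all:

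P(flag) = P(X10 ≥ 2) + P(X10 = 0)·P(Y25 ≥ 5) + P(X10 = 1)·P(Y25 ≥ 4)

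- At 20%: 0.6242 + 0.1074 × 0.5793 + 0.2684 × 0.7660 = 0.6242 + 0.0622 + 0.2056 = 0.8920.
- At 8%: 0.1879 + 0.4344 × 0.0451 + 0.3777 × 0.1351 = 0.1879 + 0.0196 + 0.0510 = 0.2585.

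None of the four figures is reproduced. The first term alone, 18.8% at 8%, is about ten times the stated 1.8% and nearly twice the whole stated type I error. The 5-of-35 limit with no early look has 14.4% type I error and 85.7% power, so it too exceeds 9.9%.

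**Step 2: allow for the 20% clause.** Y10 is the number of DLTs in patients 11 to 20.

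- If the only other limit is a running fifth DLT, stopping by patient 20 has probability P(X10 ≥ 2) + P(X10 = 0)·P(Y10 ≥ 5) + P(X10 = 1)·P(Y10 ≥ 4). At 20% this is 0.6242 + 0.0035 + 0.0325 = 0.6602. At 8% it is 0.1903.
- If the clause means 4 of the first 20, replace 5 and 4 by 4 and 3. At 20% this is 0.6242 + 0.1074 × 0.1209 + 0.2684 × 0.3222 = 0.7237. At 8% it is 0.1879 + 0.4344 × 0.0058 + 0.3777 × 0.0401, or 20.6%.

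| | Stated | 2/10 + 5/35 | With 4/20 as well |
|---|---|---|---|
| Power, 20% rate | 84% | 89.2% | 89.4% |
| Type I error, 8% rate | 9.9% | 25.9% | 26.3% |
| Stopped by patient 20, 20% rate | 37% | 66.0% | 72.4% |
| Stopped by patient 20, 8% rate | 1.8% | 19.0% | 20.6% |

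In the middle column the fifth DLT is treated as a running stop. If only the 2-of-10 limit terminates early, the last two rows are 62.4% and 18.8%. Stopping at any observed rate of 20% or more among patients 11 to 20 gives 89.8% power and 27.2% type I error. An added first-20 clause can only hold or raise the type I error. If 29 patients are entered instead of 35, the printed limits give 80.6% power and 21.7% type I error.

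**Step 3: ask whether any rule on 35 patients could give 84% and 9.9%.** By Neyman-Pearson, the randomised test on the total count bounds every sequential rule on the same patients. At 8%, P(≥6 of 35) = 0.0571 and P(≥5 of 35) = 0.1443. At 20% the same tails are 0.7279 and 0.8565.

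- Type I error 0.099 needs randomisation weight (0.099 − 0.0571)/(0.1443 − 0.0571) = 0.480. Power is then 0.7279 + 0.480 × 0.1286 = 0.790.
- Power 0.84 needs weight (0.84 − 0.7279)/0.1286 = 0.872. Type I error is then 0.0571 + 0.872 × 0.0872 = 0.133.

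So the stated pair is out of reach with 35 patients. The smallest size that allows it is 40.

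**Step 4: find a rule that does give the four figures.** Stopping at 5 of the first 20, then flagging at 6 of 40, with no 2-of-10 limit, gives early stops of 37.04% and 1.83%, power 84.07% and type I error 9.947%. All four agree with the plan after rounding.

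**The case against.** **The error is on the cautious side.** This stands. Actual power is above the stated 84%, so a toxic regimen was more likely to be caught than described. The 25.9% also applies only at exactly 8%. At assumed true rates of 5%, 2% and 1%, the printed limits flag 10.1%, 1.7% and 0.4% of trials, and sections 6.1 and 7.0 expect no grade 3-4 toxicity. The stated figures are nonetheless for 8% and 20%, and they are wrong there.

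**The 20% clause may need no count.** It can be read literally as 4 of 20, or as an introduction to the counted limits, since 2 of 10 is itself 20%. A reader might infer that 5 of 20 was meant, because 37% and 1.8% match it. That is weak evidence: those figures do not describe the printed limits at all, and 5 of 20 adds nothing once a fifth DLT is a running limit. Neither reading rescues the stated rates.

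**The fifth DLT has no stated action, so a reader might infer that patients entering after number 20 had no trial-level safety stop.** The documents do not support that. Section 8.5 sends all serious adverse events to the centre's Data Safety Toxicity Committee. Section 13.2.6 adopts the centre's monitoring plan, which is not shown and may contain a halting rule. A verdict at the end of the trial is also an ordinary use of such a limit. With accrual closed and section 6.0 capping therapy at 2 years in total, almost nothing is left to halt.

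**The source of the four figures.** A reader might conclude that they were carried over from a 40-patient design. The numerical match is exact after rounding, but the origin remains an inference. The mismatch with the printed limits does not depend on it.

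**Conclusion.** The concern holds for the stated error rates. For 2 of 10 plus 5 of 35, type I error is 25.9% against 9.9%, power 89.2% against 84%, early termination at a 20% rate 62.4% to 66.0% against 37%, and early termination in error 18.8% to 19.0% against 1.8%. Taking the 20% clause as 4 of the first 20 moves these to 26.3%, 89.4%, 72.4% and 20.6%. No interpretation of the text on 35 patients can restore 84% with 9.9%.

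The results assume independent DLTs, sequential entry, 35 treated patients and true rates of exactly 8% and 20%. They take the DLT event as given, although the protocol does not define it.

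The consequence is over-stopping, not under-protection. A stop or an adverse toxicity verdict is weaker evidence against the regimen than the plan says. Nothing here shows that such a stop occurred or that any toxicity conclusion is wrong, since the documents report no DLT counts. The missing first-20 count and the missing action at the fifth DLT are secondary points of clarity.

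**What to change.** In section 14.4.1, keep the printed limits and replace the four figures with exact values, showing both readings of the 20% clause:

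- 2 of 10 plus 5 of 35: 89.2% power and 25.9% type I error; by patient 20, 66.0% stopped at a 20% rate and 19.0% at 8% (62.4% and 18.8% from the 2-of-10 limit alone).
- With 4 of the first 20 added: 89.4%, 26.3%, 72.4% and 20.6%.

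Report any toxicity stop or adverse verdict with these rates.

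Do not choose a first-20 count or add a suspension rule now. With accrual closed, that would set a limit after the data. A future protocol that reuses the rule should state both the count and what happens at the fifth DLT.

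The cost is one exact binomial calculation and a few lines of text, with no new patients, data or committee. The stated error rates become less favourable, but the printed limits already had them.

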# 6.3 **Duration of Therapy**

In the absence of treatment delays due to adverse events, which are not generally expected, treatment may continue for 6 cycles [or can be extended for a total of 2 years if sustained a partial response (PR) or better] until one of the following criteria applies:

- Disease progression,
- Intercurrent illness that prevents further administration of treatment,
- The investigator considers it, for safety reasons, to be in the best interest of the patient.
- Unacceptable treatment related toxicity, NCI CTC AE version 4.0. Grade 3 or 4 that fails to recover to baseline or < Grade 3 in the absence of treatment within 4 weeks]
- General or specific changes in the patient's condition render the patient unacceptable for further treatment in the judgment of the investigator,
- Patient decision to withdraw from treatment (partial consent) or from the study (full consent),
- Pregnancy during the course of the study for a child-bearing participant
- Death

The date and reason for discontinuation must be documented. Every effort should be made to complete the appropriate assessments.

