#### 10.5 Additional Correlative Studies

Study has been closed to accrual on 4/12/2016 at University Hospitals. Frozen plasma/serum and peripheral blood mononuclear cells will be shipped to [name] at the Ohio State University, former PI on the trial, to undertake further analysis of inflammatory cytokines and exosomes, under a material transfer agreement (MTA). [name] will have no access to patient identifying information and the generated research data set will be linked to clinical dataset through a unique patient number. They key linking datasets will be maintained at University Hospitals. The planned studies do not include any genetic analysis. Samples would be shipped to:

Leukemia Tissue Bank Shared Resource [name]

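### The DLT stopping rule as written has none of its four stated operating characteristics: type I error is 25.9%, not 9.9%, and early termination in error is 18.8%, not 1.8%

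*Combined protocol and SAP*

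**What the plan says.** Everything is in one paragraph of Section 14.4.1 (Evaluation of toxicity). The planned number is given as "Our planned sample number is 35 evaluable patients". There are two numerical boundaries:

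- Early: "If ever 2 of the initial 10 patients exhibit DLT the study will be terminated".
- Overall: "If ever 5 of the entire 35 patients exhibit DLT the treatment will be considered too toxic".

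The properties claimed for them are: "These rules imply 84% power with 9.9% type I error to distinguish a 20% DLT rate from one not over 8" percent, and "The chance of early termination under the hypothesis of 20% DLT is 37%. The chance of early termination in error is 1.8" percent.

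The paragraph also says that, if DLTs run as high as 20%, "the study will be terminated within the first 20 patient cohort". Neither boundary uses 20 patients.

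The term DLT appears only in this paragraph and is not defined. Section 6.3 describes a toxicity that takes an individual patient off treatment ("Unacceptable treatment related toxicity, NCI CTC AE version 4.0. Grade 3 or 4 that fails to recover to baseline", or to below grade 3, within 4 weeks), but does not link it to DLT.

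**The concern.** The early-stopping figures can be checked with a single binomial tail, and they look wrong at once. At an 8% DLT rate, 2 or more events in 10 patients is not a 1-in-50 occurrence. If the early figure is that far out, the overall type I error cannot be 9.9% either, because the overall error is at least as large as the early one.

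This is the only trial-level toxicity boundary in the document; Sections 6.3, 7.0 and 8.1.1 set thresholds for individual patients. Tolerability is part of the study's stated aim in Section 2.0. A reader who trusts Section 14.4.1 would take a crossed boundary as strong evidence against the regimen, believing that an acceptable regimen is stopped early in fewer than 2% of trials and declared too toxic in fewer than 10%.

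**Working it through.** **Inputs, all from Section 14.4.1.** Early boundary: 2 or more DLTs in the first 10. Overall boundary: 5 or more in 35. Acceptable DLT rate 8%, unacceptable rate 20%. I read termination in error as termination at 8%. Monitoring continuously rather than at fixed looks changes nothing, because DLT counts can only rise.

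**Early termination** = 1 − P(X₁₀ = 0) − P(X₁₀ = 1), with X₁₀ ~ Bin(10, p).

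- p = 0.08: 1 − 0.4344 − 0.3777 = 0.1879
- p = 0.20: 1 − 0.1074 − 0.2684 = 0.6242

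**Crossing either boundary** = 1 − [P(X₁₀ = 0)·P(X₂₅ ≤ 4) + P(X₁₀ = 1)·P(X₂₅ ≤ 3)], with X₂₅ ~ Bin(25, p) for the remaining patients.

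- p = 0.08: 1 − [0.4344 × 0.9549 + 0.3777 × 0.8649] = 1 − [0.4148 + 0.3267] = 0.2585
- p = 0.20: 1 − [0.1074 × 0.4207 + 0.2684 × 0.2340] = 1 − [0.0452 + 0.0628] = 0.8920

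A simulation of 400,000 trials agrees: early 0.1874 and 0.6249, overall 0.2584 and 0.8927.

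| Quantity | Stated | Rule as written |
|---|---|---|
| Power (20% DLT rate) | 84% | 89.2% |
| Type I error (8%) | 9.9% | 25.9% |
| Early termination at 20% | 37% | 62.4% |
| Early termination at 8% | 1.8% | 18.8% |

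The type I error is 25.9/9.9 ≈ 2.6 times the stated value, and the early false stop 18.8/1.8 ≈ 10 times.

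**Could another reading recover the stated figures?** Pairs are at 20% / 8% DLT rate.

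| Reading | Early | Overall |
|---|---|---|
| Stated | 37% / 1.8% | 84% / 9.9% |
| Early means by patient 20 (2 of 10 or 5 of 20) | 66.0% / 19.0% | 89.2% / 25.9% |
| Early means any time before patient 35 | 88.0% / 25.0% | 89.2% / 25.9% |
| 5 of 35 alone | none | 85.7% / 14.4% |
| 5 of 20, then 5 of 35 | 37.0% / 1.8% | 85.7% / 14.4% |
| More than 2 of 10, more than 5 of 35 | 32.2% / 4.0% | 75.0% / 8.2% |
| 2 of 10, then 5 of 29 (evaluable number in Section 3.2) | 62.4% / 18.8% | 80.6% / 21.7% |

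None gives all four. Different DLT rates do not help either: the written rule yields 84%, 9.9%, 37% and 1.8% only at four separate rates (18.2%, 4.9%, 12.7% and 2.1% respectively).

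**Possible origin.** A grid search over two-look rules with total sizes from 20 to 80 found one rule matching all four figures: 5 or more of 20, then 6 or more of 40. It gives 84.1%, 9.95%, 37.0% and 1.8%; the 9.95% agrees with 9.9% only by truncation. This fits the stray 20-patient wording and suggests that boundaries and sample size were changed without recomputing. The protocol mentions no such rule, so this is an inference, and the finding does not depend on it.

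**The case against.** The strongest objection concerns consequence, not arithmetic. Section 10.5 records "Study has been closed to accrual on 4/12/2016 at University Hospitals". Treatment lasts at most 2 years with 30 days of toxicity follow-up, so by the version date of 10/2/2018 the rule should have had little or nothing left to govern. The written rule also stops more readily than advertised, so patients were not less protected. If no boundary was crossed, the relevant figure is the chance of missing a 20% DLT rate: 1 − 0.892 = 10.8%, against the 16% implied by the stated power, which makes the stated figure conservative. No efficacy endpoint or sample size rests on this paragraph. Finally, 25.9% counts an early stop as a too-toxic verdict, although the text attaches that verdict only to 5 of 35, which alone gives 14.4%.

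Most of this is fair and limits the practical effect. It does not make the figures true. The plan attributes them to both rules together, so the combined calculation is the natural reading, and 14.4% is not 9.9% either. Whether the overstatement matters in practice depends on whether a boundary was crossed, which the document does not say. If one was, the evidence against the regimen is weaker than a 9.9% error rate implies.

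**Conclusion.** The concern holds. All four operating characteristics are wrong for the only trial-level safety boundary, and the two false-alarm figures are wrong by factors of about 2.6 and 10. The error runs in one direction: the rule is more sensitive than stated at a 20% DLT rate, but at 8% it stops about 1 trial in 5 within the first 10 patients and crosses a boundary in about 1 in 4. The result assumes independent DLTs with a common probability, 35 patients counted for toxicity, and an 8% DLT rate as the reference for error. Since accrual is closed, the consequence is for reporting and interpreting the safety conclusion, not for enrolment.

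**What to change.** Reconcile the two boundaries, the 10- versus 20-patient wording, the sample size and the four figures in Section 14.4.1.

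- If the written rule stands, restate its properties as 89% power, 26% type I error, and early termination of 62% at a 20% DLT rate and 19% at 8%.
- If the quoted figures were the intention, the sponsor must reconcile the rule with them and recompute for the actual maximum number of patients.

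Which boundary is appropriate is for the sponsor to decide. In either case, report the safety conclusion with the corrected figures and say whether a boundary was crossed. It would also help to state which events were counted as DLTs.

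The cost is wording and arithmetic in one paragraph, plus a sentence on the DLT count. No new data are needed. The only drawback is that, for the written rule, the restated false-stop rates look less favourable.

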#### 14.4.2 Evaluation of response:

Subjects need to have received 2 or more cycles of treatment to be evaluable for response. Each patient will be assigned one of the following categories: 1) complete response, 2) partial response, 3) stable disease, 4) progressive disease, 5) early death from malignant disease, 6) early death from toxicity, 7) early death because of other cause, or 9) unknown (not assessable, insufficient data). [Note: By arbitrary convention, category 9 usually designates the "unknown" status of any type of data in a clinical database.]

All of the patients who met the eligibility criteria (with the possible exception of those who received no study medication) should be included in the main analysis of the response rate. Patients in response categories 4-9 should be considered to have a treatment failure (disease progression). Thus, an incorrect treatment schedule or drug administration does not result in exclusion from the analysis of the response rate.

#### 14.4.3 Expected Accrual

Those patients are typically managed by watchful waiting and are typically under-represented in clinical trials as they are perceived to have good prognosis. We expect to enroll 10-15 patients per year on this study.

## EASTERN COOPERATIVE ONCOLOGY GROUP (ECOG) PERFORMANCE STATUS CRITERIA

ECOG Performance Status Scale				
Grade	Descriptions			
0	Normal activity. Fully active, able to carry on all pre-disease performance without restriction.			
1	Symptoms, but ambulatory. Restricted in physically strenuous activity, but ambulatory and able to carry out work of a light or sedentary nature (e.g., light housework, office work).			
2	In bed < 50% of the time. Ambulatory and capable of all self-care, but unable to carry out any work activities. Up and about more than 50% of waking hours.			
3	In bed > 50% of the time. Capable of only limited self-care, confined to bed or chair more than 50% of waking hours.			
4	100% bedridden. Completely disabled. Cannot carry on any self-care. Totally confined to bed or chair.			
5	Dead.			

## **APPENDIX B**

## INDICATIONS FOR TREATMENT PER NCI-WG CRITERIA FOR CLL (107)

- 1. A minimum of any one of the following disease-related symptoms must be present:
  - a. Weight loss >= 10% within the previous 6 months.
  - b. Extreme fatigue (ie, ECOG PS 2 or worse; cannot work or unable to perform usual activities).
  - c. Fevers of greater than 100.5°F for >= 2 weeks without evidence of infection.
  - d. Night sweats without evidence of infection
- 2. Evidence of progressive marrow failure as manifested by the development of, or worsening of, anemia and/ or thrombocytopenia
- 3. Autoimmune anemia and/or thrombocytopenia poorly responsive to corticosteroid therapy
- 4. Massive (ie, >6 cm below the left costal margin) or progressive splenomegaly
- 5. Massive nodes or clusters (ie, >10 cm in longest diameter) or progressive lymphadenopathy
- 6. Progressive lymphocytosis with an increase of >50% over a 2-month period, or an anticipated doubling time of less than 6 months
- 7. Marked hypogammaglobulinemia or the development of a monoclonal protein in the absence of any of the above criteria for active disease is not sufficient for protocol therapy

## **APPENDIX C** PATIENT PILL DIARY FOR CYCLE 1

Patient Name Cycle #:		Pro	otocol #	_ Patient Study ID		
Cycle #: _		Mo	onth #:			
INSTRUC 1. You wil 2. You wil 1 weel 3. Record 4. If you h 5. Please b 6. Please s	CTIONS FOR Il take 8 tablets Il take 1 tablet of k after you star the date, the nu ave any comm pring your pill l ign your name	THE PATIENT: of 1000 mg curcumin pills eac of 10,000 IU vitamin D3 pills e t taking curcumin and continuo umber of tablets you took, and v ents please record them in the " bottle and this form to your phy at the bottom of the diary.	h day with or without food with a ach day with or without food with ously thereafter. what time you took them. 'Comments'' column below. rsician when you come for your n	a full glass (8 oz of water). h a full glass (8 oz of water) starting ext appointment.		
Date	Day	8 tablets of 1000 mg curcumin pills and time taken	1 tablet of 10,000 IU vitamin D3 pills and time taken	Comments		
	1					
	2		-			
	3					
	4					
	5					
	6					
	7					
	8					
	9					
	10					
	12					
	1/					
	14					
	16					
	17					
	18					
	19					
	20					
	21					
	22					
	23					
	24					
	25					
	26					
	27					
	28					

Patient's Signature:

